5.7.3 CC-486

5.7.3.1 Dose Levels

Refer to Table 3: CC-486 dose levels for guidance on dose reduction levels for each schedule. Dose reductions will be allowed from the original start dose except in Schedule 1 where no dose reductions are allowed.

Re-escalation to the higher dose level is not permitted once dose has been reduced due to toxicity with the only exception of cases considered in Table 4.

Table 3: CC-486 dose levels

Dose levels	Schedule 1	Schedule 2	Schedule 3	Schedule 4
Dose level 0 (Starting dose)	100 mg q.d. D1-21	100 mg BID D1-21	300 mg q.d D1-14	300 mg q.d D1-21
Dose level -1	No dose reduction allowed. Discontinue.	100 mg q.d	200 mg q.d.	200 mg q.d.
Dose level -2	Not applicable	Discontinue	100 mg q.d	100 mg q.d
Need for additional dose reduction	Not applicable	Not applicable	Discontinue	Discontinue

q.d.: once a day; BID: twice a day

5.7.3.2 Treatment Schedule Adjustments and Management of CC-486 Toxicities

During CC-486 treatment subjects should receive appropriate supportive care measures as deemed necessary by the Investigator considering the recommendations provided in this section.

Table 4: CC-486 dose modifications for hematologic toxicity

Toxicity	Recommendation

Grade 2-3 neutropenia on any testing*
 
* If grade ≥ 3 associated with fever at any time, the dose adjustment guidelines for grade 4 neutropenia should be enacted.
	
For Schedule 1, withhold CC-486 until recovery to \leq Grade 1. After recovery, resume CC-486 at the same dose. If no recovery from neutropenia to \leq Grade 1 is observed after 14 days of neutropenia diagnosis, permanently discontinue CC-486.
 
For Schedules 2, 3 and 4, temporarily reduce CC-486 one dose level as per Table 3 until cycle completion. If no further reduction is allowed as per Table 3, temporarily withhold CC-486 until next cycle.
 
At next CC-486 cycle:
 
 • If recovery to \leq Grade 1, re-escalate CC-486 to the previous dose (i.e. dose administered prior to the temporary reduction/interruption). • If no recovery from neutropenia to \leq Grade 1 is observed after 14 days of neutropenia diagnosis, permanently discontinue CC-486. 
Note: In cases of recurrent neutropenia (grade 3/4) after two temporary dose reductions/interruptions, CC-486 will be permanently discontinued.

Toxicity	Recommendation

Grade 4 neutropenia on a pre CC-486 hematology testing or during CC-486 treatment
	
All schedules: Withhold CC-486 until next cycle and monitor ANC until recovery to \leq Grade 1.
 
 • If recovery \leq 7 days: at next cycle, resume CC-486 at the same dose (i.e. dose administered prior to the interruption). • If no recovery $>$ 7 days: permanently discontinue CC-486 
Initiation of G-CSF should be considered by the Investigator. If initiated, administer G-CSF per institutional practice or package insert and continue until ANC recovers to $\geq 2.0 \times 10^9/L$.
 
Note: In cases of recurrent neutropenia (grade 3/4) after two temporary dose reductions/interruptions, CC-486 will be permanently discontinued. In cases where as a consequence of previous toxicity no additional dose reductions are allowed as per Table 3, CC-486 could be temporarily interrupted until next cycle.


Grade 2 thrombocytopenia on any testing
	
Hold CC-486 until Platelets recover to \leq Grade 1. Hematology to be tested periodically until recovery.
 
If delay:
 
 • \leq 7 days: resume CC-486 at same dose • 8-14 days: reduce CC-486 one dose level (if allowed per Table 3) except in Schedule 1 where treatment can be resumed at same dose, unless in the opinion of the Investigator it is in the best subject's interest to discontinue treatment with CC-486. 
If dose was previously reduced and no further dose reduction is allowed per Table 3 then CC-486 should be permanently discontinued
 
 • $>$ 14 days: permanently discontinue

Grade 3 thrombocytopenia on any testing *
 
* If grade 3 thrombocytopenia with clinically significant bleeding occurs at any time, the dose adjustment guidelines for grade 4 thrombocytopenia should be enacted.
	
Hold CC-486 until Platelets recover to \leq Grade 1. Hematology to be tested periodically until recovery.
 
If delay:
 
 • \leq 7 days: resume CC-486 at same dose • 8-14 days: reduce CC-486 one dose level (if allowed per Table 3) except in Schedule 1 where CC-486 should be permanently discontinued. 
If dose was previously reduced and no further dose reduction is allowed per Table 3 then CC-486 should be permanently discontinued
 
 • $>$ 14 days: permanently discontinue

Toxicity	Recommendation
Grade 4 thrombocytopenia on a pre-CC-486 hematology testing or during CC-486 treatment	
Hold CC-486 until Platelets recover to \leq Grade 1. Hematology to be tested periodically until recovery.
 
If delay:
 
 • \leq 7 days: reduce CC-486 one dose level (if allowed per Table 3) except in Schedule 1 where CC-486 should be permanently discontinued. 
If dose was previously reduced and no further dose reduction is allowed per Table 3 then CC-486 should be permanently discontinued
 
 • No recovery by day 7: permanently discontinue

Notes:

- When neutropenia is concomitantly observed with other toxicity/ies that require a more conservative approach, guidance on dose modifications for other AEs than neutropenia should be followed.
- The initiation of G-CSF is left at the Investigator’s discretion and should only be utilized in accordance to ASCO or ESMO recommendations. In case of G-CSF use, concurrent use (on same days) with CC-486 should be avoided: at least a two day wash-out period should be respected from CC-486 discontinuation and G-CSF initiation.
- In cases of neutropenia without any evidence of infection, prophylactic antibiotic use is left under investigator’s discretion.
- If neutropenia is associated with fever and severe diarrhea, subject should be managed appropriately according to the local practice. In case of recurrence of the diarrhea with neutropenia and fever, the continuation of the subject in the study should be discussed on a case-by-case basis with the sponsor’s medical monitor

Table 5: CC-486 dose delays/adjustments for non-hematologic toxicity

Toxicity	Recommendation

Grade 3 or 4 Nausea or Vomiting
 
Grade 3 or 4 Diarrhea
 
Grade 3 or 4 Fatigue/Asthenia
	
Hold until resolution to \leq Grade 1 and provide optimal medical management according the type and severity of toxicity (also refer to section 5.3.1).
 
If response \leq 72 hours (3 days) and recovery \leq 7 days:
 
 • Reduce CC-486 one dose level (if allowed per Table 3) except in Schedule 1 where CC-486 should be permanently discontinued. • If dose was previously reduced and no further dose reduction is allowed per Table 3 then CC-486 should be permanently discontinued • If event recurs with same/greater severity after re-challenge at a lower dose level: discontinue CC-486 
If no recovery within 7 days: discontinue CC-486/placebo
 
Note: Emesis and diarrhea should be proactively managed in all cases regardless of the grade. Anti-diarrheic treatment (including anti-diarrheic diet and use of loperamide) is recommended for the management of treatment emergent diarrhea in all cases.


Grade 3 or 4 any other clinically significant non-hematologic toxicity
	
Hold until resolution to \leq Grade 1 and provide optimal medical management according the type and severity of toxicity.
 
If recovery \leq 7 days:
 
 • Reduce CC-486 one dose level (if allowed per Table 3) except in Schedule 1 where CC-486 should be permanently discontinued. • If dose was previously reduced and no further dose reduction is allowed per Table 3 then CC-486 should be permanently discontinued • If event recurs with same/greater severity after re-challenge at a lower dose level: discontinue CC-486 
If no recovery within 7 days: discontinue CC-486/placebo

Toxicity	Recommendation
Renal dysfunction - For any unexplained reductions in serum bicarbonate levels to < 20 mEq/L or unexplained elevations of serum creatinine (or urea) > 20% from baseline	Hold until resolution to baseline level (+/- 20%) and provide optimal medical management. Reduce CC-486 dose in the next cycle of treatment to the next lower dose level except in Schedule 1 where CC-486 should be permanently discontinued. If dose was previously reduced and no further dose reduction is allowed per Table 3 then CC-486 should be permanently discontinued If similar unexplained renal and/or electrolyte disturbances subsequently persist or recur, discontinue CC-486

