5.5 Study Treatment Discontinuation

By default, subjects are treated until progressive disease as per irRECIST (Appendix 2) when study treatment must be discontinued. CA-125 increases should not be used to declare disease progression and/or study treatment discontinuation (refer to section 6.4.6.2).

In Part A and in Arm A of Part B, in case there is a need to permanently discontinue one of the study drugs (whichever the reason), the other one will also be discontinued (i.e. monotherapy with CC-486 or with pembrolizumab is not allowed in Part A and in Arm A of Part B).

The Investigator will also discontinue study treatments if any of the following conditions is met:

- Intercurrent illness or a change in subject's condition or unacceptable toxicity (see section 5.7) that warrants study treatment discontinuation according to Investigator judgment
- Any event, condition, criterion which would warrant discontinuation of pembrolizumab or CC-486 as per section 5.7.
- Any event, condition, reason which would warrant pembrolizumab or CC-486 to be held for more than the maximum acceptable delay as per section 5.7.1.
- Subject completed 24 months of uninterrupted treatment with pembrolizumab or 35 administrations of pembrolizumab, whichever is later (*Note: 24 months is calculated from the date of first pembrolizumab dose*).
- Need for additional local and/or systemic non-protocol anticancer therapy or subject receives non-protocol anticancer therapy at any time during the study treatment
- Subject's decision to withdraw study treatments
- Lost to follow up
- Death
- Pregnancy
- Investigator's decision
- Discontinuation of the study by the sponsor

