5.7 Treatment Schedule Adjustments and Adverse Events Management

5.7.1 General Rules

Regular assessment and monitoring of AEs is required throughout study treatment period and at least up until the End of Treatment visit (refer to section 7.1.1).

Toxicity will be assessed utilizing the National Cancer Institute Common Terminology Criteria for Adverse Events (NCI CTCAE) v4.03. For toxicities not specifically listed in the NCI CTCAE, the following grading will apply for assessing severity:

- Grade 1: Mild
- Grade 2: Moderate
- Grade 3: Severe
- Grade 4: Life-threatening
- Grade 5: Death related to AE

Subjects will be instructed to notify their physician immediately for any and all toxicities. Assessment of causality (chronology, confounding factors, concomitant medications, diagnostic tests, and previous experience with the study treatment) should be conducted by the Investigator prior to dose modification and/or delay whenever possible. As a general approach, it is suggested that all AEs be managed with supportive care at the earliest signs of toxicity and before delaying/reducing study drugs, when possible and if clinically appropriate.

All dose modifications should be based on the AE requiring the greatest modification and should be properly documented in source documents. Investigators may take a more conservative approach than the guidelines outlined in the protocol on the basis of clinical judgment that this is in the best interest of the subject.

In case a delay/withhold of one study drug is required, treatment with the other drug may continue according to the protocol schedule if clinically appropriate (applicable for Part A and Arm A of Part B).

Maximum acceptable delays due to adverse events related to study drug(s) are:

- For pembrolizumab: 12 weeks after prior dose of pembrolizumab
- For CC-486: the maximum number of days that dose may be withheld due to toxicity before a subject is permanently discontinued from CC-486 is 14 days (not comprising treatment off-period)

If due to an adverse event related to study drug(s) it is required to delay study treatment for more than the maximum acceptable period, then study treatment should be permanently discontinued and subject should undergo the End of Treatment visit.

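### In Schedules 1, 2 and 4, a Table 4 hold for grade 4 or febrile grade 3 neutropenia that starts on days 1-7 exceeds the 14-day maximum in 5.7.1, so a subject who recovers within 7 days is told both to resume and to stop (minor)

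*Protocol*

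**What the plan says.** Protocol 5.7.3.2, Table 4, gives one instruction for grade 4 neutropenia in all schedules: "Withhold CC-486 until next cycle and monitor ANC until recovery to" grade 1 or better. If that takes 7 days or less, the instruction is "at next cycle, resume CC-486 at the same dose (i.e. dose administered prior to the interruption"; if it takes longer, CC-486 is stopped for good. A footnote to the grade 2-3 row sends grade 3 or higher to the same rule when "associated with fever at any time, the dose adjustment guidelines for grade 4 neutropenia should be enacted". In Schedules 2, 3 and 4, the grade 2-3 row also has a hold of this kind: "If no further reduction is allowed as per Table 3, temporarily withhold CC-486 until next cycle".

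Protocol 5.7.1 sets the general limit on a CC-486 hold: "the maximum number of days that dose may be withheld due to toxicity before a subject is permanently discontinued from CC-486 is 14 days". It states its own way of counting: "is 14 days (not comprising treatment off-period".

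Protocol 5.5 lists among the conditions under which the investigator discontinues study treatments: "Any event, condition, reason which would warrant pembrolizumab or CC-486 to be held for more than the maximum acceptable delay as per section 5.7.1". For Part A and Arm A of Part B it adds that "in case there is a need to permanently discontinue one of the study drugs (whichever the reason), the other one will also be discontinued". Section 5.7.3.3, which belongs to the CC-486 part of the protocol, brings the 5.5 criteria in as reasons to stop CC-486.

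Protocol 5.3.3 fixes the on-period at 21 consecutive days in Schedules 1, 2 and 4 and at 14 in Schedule 3. Interruptions do not extend it.

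**The concern.** Table 4 sets the length of the hold by the calendar (to the next cycle) and the decision to resume by the speed of recovery (7 days). Section 5.7.1 sets the decision to stop by the length of the hold. When the hold starts early in a 21-day on-period, the length that Table 4 orders is itself over the limit, however quickly the count recovers.

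Read literally, the result is perverse. A subject held from day 7 who recovers in 2 days must stop both drugs. A subject held from day 8 who needs the full 7 days to recover resumes at the same dose.

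At stake is whether an individual subject loses both drugs permanently, on a point that two sites could decide differently. In Part A, a stop before two completed CC-486 cycles makes her non-evaluable, and 3.1 has her replaced. In the SAP's planned tables (5.1), her event would fall under CC-486 withdrawn instead of CC-486 interrupted. If Schedule 1, 2 or 4 goes forward, Arm A of Part B inherits the ambiguity.

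**Working it through.** **Inputs.** On-period length L: 21 days (Schedules 1, 2, 4) or 14 days (Schedule 3), from 5.3.3. Limit: 14 days withheld, off-period not counted, from 5.7.1. Hold: from the first withheld dose to the next cycle, from Table 4. Scheduled hematology: before each cycle and on days 8, 15 and 22, each ± 1 day, from 6.3.2.1 (Part A) and 6.3.2.2 (Arm A of Part B).

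**Check of L.** On-days times 100 mg tablets per day should give the tablets per cycle in 5.1: 21 × 1 = 21; 21 × 2 = 42; 14 × 3 = 42; 21 × 3 = 63. All four match. The 14-day limit is a rule, so there is nothing to derive.

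**Formula.** If the first withheld dose is on day d, the on-period days withheld are L − d + 1.

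| First withheld day d | Schedules 1, 2, 4 (22 − d) | Schedule 3 (15 − d) |
|---|---|---|
| 1 | 21 | 14 |
| 6 | 16 | 9 |
| 7 | 15 | 8 |
| 8 | 14 | 7 |
| 9 | 13 | 6 |

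In Schedules 1, 2 and 4, 22 − d is greater than 14 exactly when d is 7 or less. Schedule 3 cannot exceed 14.

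**The two instructions for d = 1 to 7, Schedules 1, 2 and 4.**
- Recovery within 7 days: Table 4 says resume at the same dose; 5.7.1, 5.5 and 5.7.3.3 say stop. These conflict.
- Recovery slower than 7 days: both say stop. No conflict.

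**How the window is reached.**
- Day-8 test drawn on day 7, that day's dose withheld: 22 − 7 = 15, conflict.
- The same test with the day-7 dose already taken: d = 8, 14 days, no conflict.
- Test drawn on day 8 or 9: at most 14 days, no conflict.
- Pre-cycle result: if the next cycle means the one after the cycle now due, 21 days are withheld and the rules conflict. If it means a late start of the cycle now due, recovery within 7 days gives a delay of 7 days or less and no conflict.
- Days 1-6: no scheduled test falls there, so an unscheduled one is needed, for example for fever.

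**Grade 2-3 row.** The same count applies in Schedules 2 and 4 when no reduction is left, but this route is remote. Reductions for neutropenia are temporary and are reversed on recovery. Being at the lowest level in days 1-7 therefore generally requires earlier lasting reductions for other toxicity: one in Schedule 2, two in Schedule 4 (Table 3).

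**The case against.** The strongest reply is that the specific rule governs the general one. Section 5.7.1 is headed as general rules and refers the reader to the drug-specific subsections for delays; Table 4 is that subsection and has its own stopping limit. It can also be argued that once the count has recovered, the remaining days off drug are no longer due to toxicity but follow from a fixed on-period, so they should not count toward the 14.

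This is a natural reading and may well be what was meant, but the protocol does not say so. No sentence gives Table 4 precedence. Section 5.5 is worded as something the investigator will do, while Table 4's column is headed as recommendations. Section 5.7.3.3 brings 5.5 back in from within the CC-486 section itself. Section 5.7.1 excludes the off-period from its count but does not exclude days after recovery, and the delay is one that Table 4 requires because of the toxicity.

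The reply on reach stands. A reader might infer from days 1-7 that a large share of each on-period is exposed. The testing schedule does not support that, because within the cycle only a test drawn a day early, before dosing, lands in the window. The documents give no rate of first-week grade 4 or febrile neutropenia, so no frequency can be stated.

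The reply on consequences also stands. A reader might infer that the conflict biases the Part A comparison, since Schedule 3 is exempt. The documents do not support this either. The Step 1 toxicity rule in 3.3 counts related events by grade, and the grade is the same whether CC-486 is interrupted or withdrawn. Non-evaluable subjects are replaced, and a treated subject stays in the ITT and Safety populations (SAP 3.1.1, 3.1.2).

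**Conclusion.** The conflict is real and narrow. In Schedules 1, 2 and 4, for grade 4 or febrile grade 3 neutropenia with recovery within 7 days, a first withheld dose on days 1-7 gives an ordered hold of 15 to 21 on-period days against a maximum of 14. The protocol then directs both resumption at the same dose and permanent discontinuation of both drugs, and does not say which prevails. These are two stated rules that collide; no detail is missing.

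The conclusion assumes that 5.7.1 is counted as written, with only the off-period excluded, and that Table 4's hold runs to the start of the next cycle. It does not depend on how a pre-cycle result is read. It claims nothing about how often the case arises, about the Step 1 counts or about which schedule is selected. It is a minor point, worth correcting because the instruction at issue is permanent loss of both study drugs.

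**What to change.** Add one sentence to the CC-486 bullet in 5.7.1: *This maximum does not apply when a neutropenia row of Table 4 withholds CC-486 until the next cycle; the recovery limit in that row decides (7 days for grade 4 or febrile grade 3; 14 days from diagnosis for grade 2-3).* Sections 5.5 and 5.7.3.3 then follow by reference and need no edit.

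If the sponsor does intend the stop, the grade 4 row should say so: *Schedules 1, 2 and 4, hold starting before day 8: permanently discontinue.*

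The cost is one sentence in either place, with no new data, tests or visits.

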5.7.3.3 Criteria for CC-486 Discontinuation

CC-486 needs to be permanently discontinued for any of the following:

- Any life-threatening adverse reaction
- Anaphylactic-like reaction related to CC-486 administration
- Necrotising fasciitis
- Any criteria/event listed in section 5.5 or 5.7.3

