2: Study treatment with CC-486 should start within 3 days of enrollment. The first on-treatment visit should occur on Day 1 of the 1st CC-486 cycle (subject should receive the first CC-486 dose during the visit and after the whole blood sample for DNA methylation was drawn). Afterwards, study visits are scheduled every 4 weeks \pm 3 days and should be done during the CC-486 off period as close as possible to restarting the next CC-486 cycle. Additionally, every 21 days (\pm 3 days) subjects will visit the site to receive pembrolizumab. Refer to section 5.3.3 for details on the administration of each schedule. Study treatment will continue until progressive disease according to irRECIST criteria, unacceptable toxicity, consent withdrawal or the Investigator concludes that is in the subject's best interest to discontinue (or any other withdrawal criteria is met according to section 5.5). Progression and study treatment discontinuation should not be declared on the basis of CA-125 alone.

In case there is a need to permanently discontinue one of the study drugs, the other one will also be discontinued and the subjects will undergo the End of treatment visit (and begin the Follow-up phase if applicable as per footnote 4).

3: End of Treatment visit must be scheduled 30 days (\pm 7 days) after the last administration of any study drug. The End of Treatment will be the last study visit for all subjects except those requiring follow-up according to footnote #4.

4: The subjects that will enter the follow-up phase are those who:

- Discontinue treatment for reasons different than irPD. These subjects will continue to be followed up to assess response/progression (with tumor burden assessments and CA-125) every 12 weeks (\pm 1 week) until irPD. After irPD, and provided that subject has undergone the End of Treatment visit, all subjects will be taken off the study unless requiring AE/SAE follow-up according to the next bullet.
- Discontinue treatment for any reason and have ongoing SAEs (regardless of relationship with study drugs) or study treatment-related AEs at time of the End of Treatment visit. Monitoring of these events will continue as clinically indicated until the events have resolved (or return to baseline) or in the Investigator's opinion, are unlikely to resolve due to the nature of the condition and/or the subject's underlying disease. Frequency of visits will be according to Investigator judgment.

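### Table 5 acts on a serum bicarbonate below 20 mEq/L that no scheduled chemistry measures, and in Schedules 2 to 4 its resume rule does not fit that trigger

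*Protocol*

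**What the plan says.** The last row of Protocol Table 5 (section 5.7.3.2) covers renal dysfunction. Its trigger is "For any unexplained reductions in serum bicarbonate levels to < 20 mEq/L or unexplained elevations of serum creatinine (or urea) > 20% from baseline". The bicarbonate and creatinine parts are joined by *or*, so a bicarbonate fall is enough by itself. The instruction is "Hold until resolution to baseline level (+/- 20%) and provide optimal medical management", and then "Reduce CC-486 dose in the next cycle of treatment to the next lower dose level except in Schedule 1 where CC-486 should be permanently discontinued". The row ends by stopping CC-486 if a similar unexplained disturbance persists or comes back.

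Section 5.7.3.3 includes "Any criteria/event listed in section 5.5 or 5.7.3" among the conditions that require permanent discontinuation of CC-486. For Part A and Arm A of Part B, section 5.5 adds that "in case there is a need to permanently discontinue one of the study drugs (whichever the reason), the other one will also be discontinued". Section 5.7.1 limits holds: "the maximum number of days that dose may be withheld due to toxicity before a subject is permanently discontinued from CC-486 is 14 days". A bracket after those words excludes the off-treatment period from the count.

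The scheduled blood chemistry has the same seven analytes wherever it is listed: creatinine, AST, ALT, alkaline phosphatase, bilirubin, glucose and TSH. The lists are in the synopsis (Safety Assessments), footnote 7 of Tables 6 and 7, and sections 6.3.1, 6.3.2.1, 6.3.2.2 and 6.4.5. The synopsis reproduced in SAP Appendix 6.1 agrees. On timing, Table 6 footnote 2 says "Afterwards, study visits are scheduled every 4 weeks", and Table 7 footnote 2 sets the same interval for Arm A. In Table 4 the thrombocytopenia rows add "Hematology to be tested periodically until recovery"; the renal row of Table 5 has no such line.

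**The concern.** A symptomatic toxicity announces itself, but an isolated laboratory fall is found only if someone runs the test. A site that follows the schedule exactly would not see a low bicarbonate in a subject whose creatinine stayed within 20% of baseline. Two subjects with the same value could then be managed differently because one hospital's routine panel includes bicarbonate and another's does not.

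The resume rule needs a baseline bicarbonate that the protocol does not collect. Even where a local baseline exists, the rule pairs a fixed trigger with a resolution limit relative to baseline, so the two need not meet.

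At stake is consistent application of a dose rule: a hold and one dose level in Schedules 2 to 4, and the loss of both drugs in Schedule 1. Schedule 1 is one of four Part A cohorts (at least 5 evaluable subjects each) and reaches Part B only if selected.

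**Working it through.** The plan states no figure here to reproduce. There are three checks.

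**1. Scheduled measurements over the planned treatment phase.** The inputs are the 6-month treatment phase (synopsis), taken as 26 weeks, and chemistry at screening, before each CC-486 cycle and at End of Treatment (Tables 6 and 7). The first cycle is not counted separately, because the repeat is waived when screening chemistry was done within 7 days.

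- Creatinine: 1 (screening) + 6 (weeks 4, 8, 12, 16, 20, 24) + 1 (End of Treatment) = 8.
- Bicarbonate: 0.

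**2. Trigger against resume limit.** Let B be baseline. For a fall, the resume limit is 0.8 × B and the trigger is any value below 20. The two coincide when 0.8 × B = 20, so B = 20 / 0.8 = 25 mEq/L. The documents give no baseline bicarbonate, so the values of B below are assumptions.

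| Assumed B (mEq/L) | 0.8 × B | Result |
|---|---|---|
| 22 | 17.6 | 17.6 to < 20 both triggers and counts as resolved |
| 24 | 19.2 | 19.2 to < 20 both triggers and counts as resolved |
| 25 | 20.0 | limits meet; no conflict |
| 26 | 20.8 | 20 to < 20.8 does not trigger but does not end a hold |
| 28 | 22.4 | 20 to < 22.4 does not trigger but does not end a hold |

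For creatinine the trigger is above 1.20 × B and resolution is at or below 1.20 × B. These are complementary, so the mismatch is specific to bicarbonate. It does not arise in Schedule 1, where CC-486 stops and is not resumed.

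**3. Hold limit against the next scheduled chemistry.** Only on-period days count towards the 14-day limit. Suppose a hold starts on cycle day d and lasts to the end of the on-period.

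- Schedules 2 and 4 (21 days on): counted days = 21 − d + 1 = 22 − d. At d = 8 this is 14, within the limit. At d = 7 it is 15. The limit is therefore exceeded before the next pre-cycle chemistry only if the hold starts on days 1 to 7.
- Schedule 3 (14 days on): counted days = 14 − d + 1, which is at most 14. The limit is not exceeded before the next pre-cycle chemistry.

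**The case against.** The best defence is that detection is not left empty. The protocol allows further tests when clinically indicated or when they are standard of care, and requires the investigator to appraise abnormal results. It also calls for a metabolic panel in new type 1 diabetes or grade 3-4 hyperglycemia (section 5.7.2.3). The instructions in Table 5 are headed as recommendations. This stands against a reading that the trigger could never be applied. It does not close the gap: the metabolic panel is event-driven with unspecified contents, discretion cannot act on a value nobody measured, and section 5.7.3.3 makes the Schedule 1 stop binding.

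The consequence of the overlap is limited. Resumption is at a reduced dose, and a value still below 20 can be handled under the rule on persistence or recurrence. That stands.

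A reader might set the 4-week chemistry interval against a 14-day hold and infer that every hold runs out before the next test. The exclusion of off-period days rules this out for Schedule 3 and for later holds in Schedules 2 and 4. The missing re-test line also applies to creatinine, so it is not a bicarbonate defect.

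A reader might also call urea a second omission. It appears only in brackets as an alternative to creatinine, which is measured.

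Finally, pre-cycle visits fall in the CC-486 off-period, so a fall that recovers quickly could be missed even with the added test. That is a fair limit on the fix, but creatinine is sampled at the same visits.

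**Conclusion.** The point holds as a minor safety-monitoring inconsistency that is cheap to repair. A stand-alone dose-modification trigger rests on an analyte scheduled 0 times, against 8 for creatinine over 6 months. In Schedules 2 to 4 its resume rule is also mismatched, in one direction for baselines below 25 mEq/L and in the other above 25. The measurement gap follows directly from the protocol's lists. The numerical examples of the mismatch rest on assumed baselines.

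The documents give no frequency of isolated, unexplained bicarbonate below 20 mEq/L, so the number of subjects affected cannot be estimated. Because stopping CC-486 also stops pembrolizumab, a reader might infer bias in treatment duration or in the efficacy comparison. Without a frequency the documents do not support that, and no effect on endpoints or power is claimed.

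**What to change.** 1. Add serum bicarbonate to the blood chemistry at screening and before each CC-486 cycle, in Part A and in Arm A of Part B, on the sample already drawn. Edit the synopsis, footnote 7 of Tables 6 and 7, and sections 6.3.1, 6.3.2.1, 6.3.2.2 and 6.4.5. Part B subjects are screened before their arm is known, so a screening value there means testing all of them once.
2. For the bicarbonate trigger in Table 5, define resolution as at least 20 mEq/L, or as return to baseline if baseline was below 20. Inclusion criterion 11 sets no bicarbonate limit, so a low baseline is possible. Leave the creatinine (or urea) trigger and its resume limit unchanged.
3. Optionally, add a line to the whole renal row asking for re-testing until recovery. It matters for holds starting in the first week of a cycle in Schedules 2 and 4.

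**Cost.** There would be 7 extra results per CC-486 subject over 6 months (1 screening + 6 pre-cycle), or 8 with End of Treatment. If everyone stays 6 months, that is 20 × 7 = 140 results for the minimum Part A enrollment and 75 × 7 = 525 for Arm A (160 and 600 with End of Treatment). Screening Arm B as well adds 75 × 1 = 75; screen failures are not counted. Items 1 and 2 need no extra visit or venipuncture; re-tests under item 3 would add draws for held subjects. The change needs a formal amendment (section 9.4) and one more parameter in the laboratory summaries of SAP section 3.5.3. It may also produce a few more holds, reductions or Schedule 1 stops, all already prescribed. A Part A subject stopped before completing two CC-486 cycles would be non-evaluable and replaced (section 3.1).
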